3.2. Study Schema

3.3. Timing of assessments

	Prior to registration	1 st Colonoscopy	Post- colonoscopy	Prior to repeat colonoscopy	Repeat colonoscopy	Post repeat colonoscopy	End of trial)*
Written Informed consent	х						
Review inclusion / exclusion criteria	х			x			
Colonoscopy findings/ outcomes		x			x		
Histology outcomes			х			х	
Blood sample collection					х		
Methylation outcomes			х			х	
Stool sample collection					х		
Therapeutic endoscopy (if required)			х			х	
Surgery (if required)			х			х	
Adverse event evaluation		х	х		х	х	х

^{*} After 4-12 months: Long term follow up of this cohort of patients will be undertaken to assess late conversion rate to neoplasia. This will be undertaken outside of the study.

4. ELIGIBILITY

4.1. Centre eligibility

ENDCaP-C will aim to recruit 1000 patients from up to 37 centres in the UK. Eligible centres will be those having active chronic IBD endoscopic surveillance programmes.

4.2. Patient Inclusion and Exclusion Criteria

Inclusion criteria

- Diagnosis of either:
 - Chronic ulcerative colitis with symptoms for over 10 years duration
 - Primary Sclerosing Cholangitis
- On the surveillance programme and undergoing a routine colonoscopy during the study period
- Willing to accept the possibility of an additional colonoscopy between 4 and 12 months after registration.
- No previous history of colorectal cancer
- Aged 18 years or over
- Be able and willing to provide written informed consent for the study

Exclusion criteria

- Bowel obstruction
- Patients in whom it is not possible to undergo complete colonoscopies
- Patients with proctitis only
- Unable to give written informed consent
- Less than 18 years of age
- For UC only patients:
 - Patients with fulminant colitis
 - Crohns colitis patients
 - o Patients with unclassified IBD
 - o Patients with microscopic colitis

5. CONSENT AND RECRUITMENT

5.1. Recruitment:

1000 patients will be recruited from up to 37 centres in the UK. Recruitment in the West Midlands will be facilitated by the West Midlands Inflammatory Bowel Disease (IBD) network, with 15000 IBD patients of whom 7,000 are on a centralised database. The Birmingham and Black Country IBD Network comprises; Queen Elizabeth, Heartlands and Solihull, Good Hope, City and Sandwell, New Cross, Russell's Hall, and Manor Hospital, Walsall. Other centres, undertaking protocol driven surveillance, based on national guidelines will also be invited to participate.

Eligible participants will be provided with study information, possibly with their appointment letter. Identification of those who have consented to participation will be through stickers on the patient notes. Team training meetings will be provided at each centre, and the information provided will be reinforced by investigator meetings and newsletters.

5.2. Informed consent

The study will be conducted in accordance with the Research Governance Framework for Health and Social Care and the International Conference on Harmonisation of Good Clinical Practice.

At the pre-assessment or colonoscopy appointment, the patient will meet with a consultant gastroenterologist or surgeon to discuss the study. Participants who potentially fulfil the inclusion criteria for this trial must have their eligibility confirmed by a medically qualified doctor with access to and a full understanding of the potential participant's medical history. The confirmation of eligibility must be documented in the patient's notes and on the registration form. Eligibility must be confirmed before registration.

The patient's written informed consent to participate in the study must be obtained before registration and after a full explanation of the study has been given. Written informed consent will be obtained by a trained member of the research team (with clinical training, GCP training, knowledge of the study protocol, and delegated authority from the local PI). Within the ENDCaP-C study, it is anticipated that consent will usually be obtained by a surgeon, gastroenterologist or research nurse at site.

Once written informed consent is obtained the original copy should be kept in the ENDCaP-C study site file, one given to the patient, one kept in the patient's notes and one sent to the ENDCaP-C Study Office. Patients will give their explicit consent for the movement of their consent form, giving permission for the study office to be sent a copy. This will be used to perform in-house monitoring of the consent process.

Informed consent must be obtained before any study-related procedures are undertaken.

If new information becomes available which may be relevant to the patient's consent, forms will be revised and informed consent sought again. The ENDCaP-C Study Office will advise when this is required.

5.3. Registration

Once eligibility has been confirmed and after written informed consent has been obtained, patients can be registered into the study.

Patients are registered into the study online at the ENDCaP-C website, https://www.Trials.bham.ac.uk/ENDCaPC

Or by telephone call to the BCTU registration service ([name])

Telephone registration is available Monday-Friday 09:00-17:00.

Online registration is available 24 hours a day, 7 days a week apart from short periods of scheduled maintenance and occasional network problems.

For the secure online registration website, each investigator will be provided with a unique username and password.

Registration notepads will be provided to investigators and should be used to collate the necessary information prior to registration. The person registering will need to answer all of the questions before registration and a study number is given.

5.4. Informing the participant's GP

With the patient's prior consent, their General Practitioner (GP) will also be informed that they are taking part in the study. A GP Letter is provided electronically for this purpose.

5.5. Screening logs and acceptance rate

A screening log will be kept of all eligible patients, including those who decline to take part with the reason for declining. Details recorded will include the reason for non-registration and the date this was

determined. This will establish the acceptance rate of the study by patients and the generalizability of the study participants.

6. TESTS AND PROCEDURES

6.1. Standard colonoscopy surveillance and histology

All patients will undergo a protocol-driven surveillance colonoscopy by a named colonoscopist as per usual NHS care.

During this procedure, routine biopsy samples will be taken. As a minimum, our requirements are for two samples from the left side of the colon, two from the right side of the colon and one from the rectum. We do not object to additional biopsies being taken and sent to us if this is preferred at a site. Each biopsy will involve two "bites" from the mucosa using a spiked endoscopy forceps as is current standard practice.

If it is not possible to collect all the required biopsy samples at the baseline colonoscopy due to, for instance, fulminant colitis or bowel obstruction not detected prior to colonoscopy, the patient may be invited approximately 6 weeks later for a repeat colonoscopy and this colonoscopy can be used as the baseline. These patients would remain in the study and would not be withdrawn.

Biopsy samples should be embedded in paraffin and processed and analysed as per local practice. It is important that biopsies from different sites (left, right and rectum) should not be embedded into the same block and so we expect a minimum of THREE blocks, one per site. If this is not possible or unavoidable, guidance on the how to identify the appropriate biopsies must be provided.

As these samples are those taken as part of routine practice (i.e. they are not additional blocks being taken specifically for the ENDCaP-C study), the blocks will be returned to site at the end of the trial and will not be exhausted. Blocks for an individual patient can be returned earlier if required for clinical reasons. Please contact the ENDCaP-C Study Office to discuss this if required.

The ENDCaP-C Study Office will send out instructions on sample requirements to all participating centres.

Analysis of FFPE sections from biopsy material will be coordinated by a named lead pathologist at each centre. If dysplasia is detected in any of the biopsies, patients will be offered endoscopic or surgical resection as decided by their MDT. Patients offered endoscopic or surgical resection will also have details of the type (endoscopy, laparotomy, and laparoscopy) and extent of resection recorded on the CRF along with updated pathological findings.

6.2. Index Test: Adjunctive methylation

The index test will be the DNA methylation panel of markers defined in Module 1 and refined as a quality-assured clinical assay in Module 2. These work packages will have defined the combination of genes and loci which result in a classification of hypermethylation.

After local histological analysis, FFPE blocks will be sent to the ENDCaP-C Trial Office. Blocks will be identified by study number and one other identifier. The blocks will then be transferred to the pathology department at the Queen Elizabeth Hospital Birmingham where all blocks will undergo a central histology review. DNA will be extracted and transferred to the Birmingham United Molecular Pathology (BUMP) laboratory at Birmingham Women's Hospital for methylation analysis. Methylation results will be held on the secure ENDCaP-C study database. This will ensure the reference standard is undertaken blinded to the methylation result. The methylation results will not be released to patients (in the trial) or clinicians during the study period.

6.3. Early Reference Standard (see 3.6, Study Schema)

The early reference standard will be the histological analysis obtained from the standard surveillance colonoscopy at trial entry as detailed above.

6.4. Late Reference Standard (see 3.6, Study Schema)

All histologically negative patients with positive methylation status (test positives) will be identified by the ENDCaP-C Study Office and will be invited to undergo early repeat colonoscopy. Twice as many histologically negative patients that have negative methylation status will be randomly selected without matching (test negatives) by the ENDCaP-C Study Office and also will be invited to undergo early repeat colonoscopy. The late reference standard colonoscopy will be undertaken 4-12 months after the standard colonoscopy, blinded to methylation status. This reference assessment will be standardised using dye spray and targeted biopsy to maximise dysplasia detection, and should be performed by nominated, experienced colonoscopists at each site.

During this procedure, biopsy samples will be taken. As with the standard colonoscopy at trial entry, our requirements are for two samples from the left side of the colon, two from the right side of the colon and one from the rectum. We do not object to additional biopsies being taken and sent to us if this is preferred at a site. Each biopsy will involve two "bites" from the mucosa using a spiked endoscopy forceps as is current standard practice.

Biopsy samples should be embedded in paraffin and processed and analysed as per local practice. It is important that biopsies from different sites (left, right and rectum) should not be embedded into the same block and so we expect a minimum of THREE blocks, one per site. If this is not possible or unavoidable, guidance on the how to identify the appropriate biopsies must be provided.

The ENDCaP-C Study Office will send out instructions on sample requirements to all participating centres.

After local histological analysis, FFPE blocks will be sent to the ENDCaP-C Trial Office. Blocks will be identified by study number and one other identifier. The blocks will then be transferred to the pathology department at the Queen Elizabeth Hospital Birmingham where all blocks will undergo a central histology review. DNA will be extracted and transferred to the Birmingham United Molecular Pathology (BUMP) laboratory at Birmingham Women's Hospital for methylation analysis. Methylation results will be held on the secure ENDCaP-C study database. This will ensure the reference standard is undertaken blinded to the methylation result. The methylation results will not be released to patients (in the trial) or clinicians during the study period.

If dysplasia is detected following the repeat colonoscopy, patients will be offered endoscopic or surgical resection as decided by their MDT, in accordance with the protocol for usual care. Participants offered endoscopic or surgical resection will also have details of the type (endoscopy, laparotomy, and laparoscopy) and extent of resection recorded on their CRF along with updated pathological findings.

6.4.1 Stool sample collection

All patients scheduled to attend for the late reference standard colonoscopy and who have consented to sample collection will be sent a stool collection kit in the post with instructions to bring a stool sample (taken before bowel preparation) to the hospital on the day of the endoscopy. This will be used to test for Wnt antagonist methylation.

The ENDCaP-C Study Office will send out instructions on sample requirements to all participating centres.

6.4.2 Blood sample collection

At the time of the late reference standard colonoscopy, an addition 10ml venous blood sample will be taken patients who have consented to sample collection. This will be used to test for Wnt antagonist methylation in serum.

The ENDCaP-C Study Office will send out instructions on sample requirements to all participating centres.

6.5. Avoidance of Study Biases:

The generalisability of the study will be assured by aiming to recruit a consecutive sample of patients attending for routine surveillance, who fall within the high risk category. Information will be collected on risk factors in all study patients and investigate whether the diagnostic value of methylation varies according to patient characteristics.

Misclassification bias can occur in test accuracy studies where the reference standard test is inaccurate. The initial colonoscopy will be a routine surveillance procedure, making the study a pragmatic one which assesses the incremental value of methylation over and above standard current practice. The reference standard colonoscopy will be of the highest quality possible, utilising dye spray to increase dysplasia detection and will be restricted to experienced, nominated colonoscopists at sites. In addition, this colonoscopy will occur 4-12 months after the initial colonoscopy, which will increase the chances of finding dysplasia that was initially not detected (i.e. identifying patients with false negative initial histology). Whilst there is a risk that new dysplasia may develop during this period, this time period has been chosen to minimise the risk. This should not introduce bias as it should be equal in both methylation test positives and negatives. Long term follow up of this cohort of patients will be undertaken, to assess late conversion rate to neoplasia. This will be undertaken outside of this study.

Reference standard colonoscopies will only be undertaken in a sample of methylation test negatives. As this sample will be chosen randomly without matching it should be representative of all test negatives, and the results not suspect to partial verification bias.

It is acknowledged that verification bias cannot be completely eliminated due to the fact that the histologist will be aware that any repeat colonoscopy will consist of both test positives and test negatives. Hence to minimise this bias so that histologists cannot base their decision criteria for histological classification by knowledge of the allocation ratio, we will match the numbers of controls recruited at the study level and not within each hospital.

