A diagnostic test has been developed to identify IBD patients at high risk for development of colon cancer based on the methylation of an array of relevant genes. Briefly, to get to this stage, a retrospective diagnostic case-control study was performed. A large cohort of formalin fixed paraffin embedded (FFPE) biopsies obtained from biopsies obtained at routine surveillance colonoscopies for patients with chronic ulcerative colitis were identified from histology archives in six hospitals. The cohort was structured to include adequate samples from cases recorded as having neoplasia and dysplasia were identified, as well as those from controls without either neoplasia or dysplasia, to be able to create a reliable classifier. DNA was extracted from these blocks and then bisulphite pyrosequencing was used to measure methylation at multiple CpG positions within various wnt antagonists. As hypermethylation and epigenetic silencing of secreted Wnt antagonists occurs early in tumour development and is thought to be a 'gatekeeper' event, essential for large bowel neoplastic change, this provides a sensitive marker for the development of neoplasia. This was followed by the development and validation of a quality-assured, clinically applicable test for a panel of biomarkers.

The aim of this study is to assess the validity of this test in patients with ulcerative colitis undergoing surveillance colonoscopy. The accuracy of the methylation assay will be established through evaluation of its ability to detect dysplasia missed by histology within a prospective cohort study allowing prediction of its likely clinical utility. This study will also establish the generalisability of the assay as it is introduced alongside routine surveillance across at least 8 different hospitals. The feasibility of testing for hypermethylation of secreted Wnt antagonists in serum and faecal samples will also be investigated.

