2. OBJECTIVES AND OUTCOMES

2.1. Objectives

ENDCaP-c is multi-centre cohort study with the following objectives:

Primary objective:

• To estimate prospectively the ability of the methylation assay to detect pre-cancerous lesions (dysplasia) missed by histology within a surveillance programme for colitis associated neoplasia (CAN).

Secondary objectives:

- To estimate the incremental accuracy of methylation testing over histology within a CAN surveillance programme and gain experience of its applicability in the clinical setting.
- To evaluate the feasibility of testing for hypermethylation of secreted Wnt antagonists in serum and faecal samples, and if feasible, to assess their accuracy

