3.1. Test Accuracy Study Design

ENDCaP-C is a prospective diagnostic test accuracy study. An outline of the test accuracy study is shown in the study schema. It is designed to generate a comparison of measurements obtained by the index test with those obtained by reference standard. In this way the accuracy of the index test can be estimated. A reference standard is a test that confirms or refutes the presence or absence of disease beyond reasonable doubt. Therefore it is sometimes also known as the gold standard. The methylation test is the index test whereas the reference standard will be histology at 4-12 months after the methylation test.

In the study the results of the index test will first be compared with histology of biopsy samples taken at the first standard surveillance colonoscopy (labelled "diagnostic value of the test" in the study schema below) and then with the reference standard colonoscopy (labelled "prognostic value of the test" in the study schema). The second comparison is the primary comparison for the study as the reference standard colonoscopy used at this point will be of the highest quality possible, utilising dye spray to increase dysplasia detection and restricting to nominated, experienced colonoscopists at each site. In addition this colonoscopy will occur 4-12 months after the initial colonoscopy, which will increase the chances of finding dysplasia that was initially not detected (i.e. identifying patients with false negative initial histology).

In order to ensure efficiency in the study design, whilst all patients with positive tests for methylation will undergo the reference standard colonoscopy, only a sample of those with negative tests will be selected for reference standard colonoscopy. The rationale for this is given in the sample size section below.

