10. OUTCOME MEASURES

10.1. Protection from bias

The generalisability of the study will be assured by aiming to recruit a consecutive sample of patients attending for routine surveillance who fall within the high risk category. We will collect information on risk factors in all study patients and investigate whether the diagnostic value of methylation varies according to patient characteristics.

Misclassification bias can occur in test accuracy studies where the reference standard test is inaccurate. Whilst we are ensuring the initial colonoscopy is a routine surveillance procedure to ensure the study is pragmatic and will address the incremental value of methylation over and above standard current practice, the reference standard colonoscopy will be of the highest quality possible, utilising dye spray to increase dysplasia detection and restricting to experienced, nominated colonoscopists at each site. In addition this colonoscopy will occur 4-12 months after the initial colonoscopy, which will increase the chances of finding dysplasia that was initially not detected (i.e. identifying patients with false negative initial histology). Whilst there is a risk that new dysplasia may develop during this period, we have chosen a time period to minimise this risk, which should not introduce bias as it should be equal in both methylation test positives and negatives. Long term follow up of this cohort of patients will be undertaken, to assess late conversion rate to neoplasia. This will be undertaken outside of this study.

We have elected only to undertake reference standard colonoscopies in a sample of methylation test negatives. As this sample will be chosen randomly without matching it should be representative of all test negatives, and the results not suspect to partial verification bias.

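### New dysplasia arising between the two colonoscopies biases the accuracy estimates for missed dysplasia even if it is equally common in test positives and negatives; Protocol 6.5 and 10.1 say it should not

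*Protocol*

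**What the plan says.** Protocol 2.1 gives the primary objective as the ability of the assay to "detect pre-cancerous lesions (dysplasia) missed by histology within a surveillance programme". Section 3.1 compares the methylation result first with histology from the same colonoscopy and then with the later reference colonoscopy, and states: "The second comparison is the primary comparison for the study". It labels that later comparison prognostic.

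Section 6.5 gives the gap ("this colonoscopy will occur 4-12 months after the initial colonoscopy") and concedes the difficulty: "Whilst there is a risk that new dysplasia may develop during this period, this time period has been chosen to minimise the risk". It then dismisses it: "This should not introduce bias as it should be equal in both methylation test positives and negatives". Section 10.1 repeats the reasoning: "which should not introduce bias as it should be equal in both methylation test positives and negatives".

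The primary measures in 10.2.1 are the PPV and the DOR, both against dysplasia at the 4-12 month colonoscopy. Neither the outcome definitions nor the analysis in 11.3 distinguishes a missed lesion from a new one.

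**The concern.** Two steps in the dismissal need checking. The first is the inference: does equal incidence leave the accuracy measures unbiased? Equal incidence would cancel from a simple difference in risk to a first approximation, but PPV, NPV, sensitivity and the DOR are not differences in risk.

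The second is the premise. Section 1.2 says that silencing of these genes comes early in tumour development and may be a gatekeeper step, so that "this provides a sensitive marker for the development of neoplasia". It also describes the test as identifying patients at high risk of developing colon cancer. If that is right, methylated patients should acquire more new dysplasia than unmethylated ones, not the same amount.

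At stake is what a positive result may be said to show. The objective claims detection of missed lesions, while the data will hold missed and new lesions together.

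**Working it through.** **Inputs (Protocol 11.1).** Of 1000 patients, 40 have dysplasia found by histology and 40 have it missed. The test finds 20 of the 40 missed and gives 46 false positives among 920 free of dysplasia. So there are 66 test positives (20 with, 46 without dysplasia) and 960 − 66 = 894 test negatives (20 with, 874 without). Of these, 132 are verified, with 3 expected positive and 129 negative. The PPV threshold is 15%, P<0.05, sidedness not stated.

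**The plan's own figures.** PPV = 20/66 = 30.3%. One-sample normal approximation, n = 66, two-sided 0.05, 30% against 15%: power 87.1%, matching the stated 87%. Expected positives among 132 test negatives: 132 × 20/894 = 2.95, matching the stated 3. DOR on planned counts: (20 × 129)/(46 × 3) = 18.7 (19.0 on the full cohort).

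**Equal incidence q.** The protocol gives no q, so these values are assumptions. New lesions arise among those free of dysplasia at the first colonoscopy:
- TP = 20 + 46q, FP = 46(1 − q)
- FN = 3 + 129q, TN = 129(1 − q)

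At q = 2%: TP 20.92, FP 45.08, FN 5.58, TN 126.42, so DOR = (20.92 × 126.42)/(45.08 × 5.58) = 10.5.

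| q (both groups) | PPV | NPV | DOR |
|---|---|---|---|
| 0 | 30.3% | 97.7% | 18.7 |
| 0.5% | 30.7% | 97.2% | 15.6 |
| 1% | 31.0% | 96.7% | 13.4 |
| 2% | 31.7% | 95.8% | 10.5 |

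Sensitivity, from the full cohort with FN = 20 + 874q, falls from 50% to 20.46/(20.46 + 28.74) = 41.6% at 1%, and to 20.92/(20.92 + 37.48) = 35.8% at 2%. Specificity stays at 95%. The DOR and sensitivity move most because they rest on few false negatives.

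If the true DOR is 1, both groups share one risk before and after adding q, so the DOR stays 1.

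**Unequal incidence (assumed 5% in test positives, 1% in test negatives).**
- Test no better than chance for missed lesions: both groups have risk 40/960 = 4.17%. Positives become 0.0417 + 0.9583 × 0.05 = 8.96%; negatives 0.0417 + 0.9583 × 0.01 = 5.13%. Observed DOR = (0.0896/0.9104)/(0.0513/0.9488) = 1.8.
- Planned performance, full cohort: PPV rises to (20 + 2.3)/66 = 33.8%, while the DOR still falls, from 19.0 to 15.4. For it to stay at 19, incidence in positives would have to be about 11 to 13 times that in negatives (for incidence in negatives from 2% down to 0.5%).

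**The PPV test.** Suppose the PPV for missed lesions is exactly 15%. With incidence q in the remaining test positives, the observed proportion has expectation 0.15 + 0.85q, which is 16.7% at q = 2%. Exact binomial chance of declaring PPV over 15%, n = 66:

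| Rule | q = 0 | q = 2% |
|---|---|---|
| 17 or more positive (exact, two-sided 0.05) | 1.6% | 4.1% |
| 16 or more positive (exact, one-sided 0.05) | 3.2% | 7.4% |

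**The case against.** The strongest reply is that the primary outcomes in 2.2.1 and 10.2.1 are simply dysplasia at the 4-12 month colonoscopy, with no condition that it was missed earlier. For that outcome a new lesion is part of the target and there is no bias. Section 3.1's prognostic label fits this reading, and so does 11.1, which argues for 15% as a useful yield from a further colonoscopy. This stands, and it points to the remedy. It does not rescue the sentence, because the objective says missed, and 3.1 and 6.5 justify the gap as a way of finding false negative initial histology.

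It is also fair that the protocol acknowledges the risk, chose the window to limit it, and says only that bias should not arise. The PPV shift under equal incidence is small, 1.4 points at 2%, and the pull on the DOR is conservative.

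Three stronger readings are tempting but unsupported.
- A reader might infer that the PPV test could succeed on new disease alone. It could not, realistically: with a missed-lesion PPV of zero, the chance of declaring PPV over 15% is below 0.001% at an assumed 5% incidence and at most 0.06% even at 10%.
- A reader might take unequal incidence as established. Section 1.2 hedges the gatekeeper role, and its field-change data come from patients who already had synchronous neoplasia. Higher incidence in test positives is plausible, not shown.
- A reader might expect a split by interval to isolate missed lesions. It cannot: 3.1 and 6.5 say that the delay also improves detection of lesions initially missed, and about 3 false negatives are too few to divide. The absence of an interval analysis from the protocol is not a defect either, since it could sit in an SAP that was not available.

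**Conclusion.** The statement in 6.5 and 10.1 is wrong as written for the stated objective. The direction under equal incidence follows from arithmetic for any incidence above zero when the true DOR exceeds 1: PPV up slightly, NPV and sensitivity down, DOR toward 1. The size depends on an incidence that the protocol does not give. At an assumed 1-2%, the DOR falls from 18.7 to between 13.4 and 10.5, and sensitivity from 50% to between 41.6% and 35.8%.

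The equality premise also sits badly with the protocol's own rationale. If it fails in the direction that rationale suggests, PPV overstates the yield of missed lesions, and the DOR can exceed 1 with no ability to find them (1.8 at the assumed 5% against 1%). At the null PPV, the effect on the test is modest: 1.6-3.2% becomes 4.1-7.4% at an assumed 2%. The point limits what the trial may conclude; it does not invalidate the design.

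**What to change.** - Delete the no-bias statement in 6.5 and 10.1. In its place say that new dysplasia in the gap raises PPV, lowers NPV and sensitivity, and, if incidence is equal, moves the DOR toward 1; and that higher incidence in test positives would further inflate PPV as a measure of missed lesions and could raise the DOR.
- Align the primary objective (synopsis and 2.1) with the primary outcome (2.2.1 and 10.2.1): define the target condition as dysplasia detected at the 4-12 month reference colonoscopy, whether missed or new. Limit the primary claim to that, and report sensitivity and NPV for the same target.
- Treat any analysis by time between colonoscopies as exploratory, and do not present it as an estimate for missed dysplasia.

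The cost is protocol wording and a somewhat narrower conclusion. Recruitment, procedures and the planned numbers need not change.
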